**Figure 6-1 Schematic of the Study Design**

661/770: TEZ/IVA; 770: IVA; PBO: placebo.

Subjects who prematurely discontinue study drug treatment will continue to complete all other scheduled study visits for assessment of efficacy through the end of the Treatment Period in which discontinuation occurred.

## 6.2 Sample Size and Power

The primary efficacy endpoint is the absolute change in ppFEV1 from study baseline to the average of the Week 4 and Week 8 measurements in each Treatment Period.

The null hypotheses to be tested are that the mean absolute change from study baseline in ppFEV1 to the average of the Week 4 and Week 8 measurements is the same for (i) TEZ/IVA and placebo; and (ii) IVA monotherapy and placebo.

Assuming a standard deviation (SD) of 7 percentage points, 30 subjects per sequence are needed to have at least 90% power to detect a 3 percentage point treatment difference between TEZ/IVA and placebo when the mean values of the primary endpoint are being compared. A 2-sided significance level of 0.05 was used in the sample size calculations. Accounting for the testing strategy, the proposed sample size will yield approximately an 85% chance of observing a statistically significant difference between IVA monotherapy and placebo for the primary endpoint, under the assumption that IVA monotherapy is also 3 percentage points better than placebo (refer to Section 8.3.2.3 for a detailed description of the testing strategy). The sample size estimate was based on 10,000 simulation runs with an incomplete block design assuming no dropouts. In the simulation, the correlation between responses to the 2 treatments within a subject was assumed to be zero. After adjusting for an assumed dropout rate of 10%, the sample size was increased to 34 subjects per sequence (204 total subjects).

## 6.3 Randomization

Approximately 204 subjects (34 per sequence) who meet eligibility criteria will be stratified by age at the Screening Visit (<18 versus ≥18 years of age), ppFEV1 severity determined during the Screening Period (<70 versus ≥70), and type of residual function mutation on the second CFTR allele (Class V non-canonical splice mutation versus Classes II to IV residual function mutation; see section 16 of the clinical study protocol), and then randomized (1:1:1:1:1:1) to 1 of the 6 treatment sequences, as shown in Section 6.1. A minimum of 25% of enrolled subjects will carry a Class II to IV mutation on the second CFTR allele (see Section 10.8). Enrollment into the non-canonical splice strata will be limited to no more than 75% of total enrollment.

An IWRS will be used to assign subjects to treatment sequence and to ensure enrollment of at least 25% of subject with Class II to IV residual function mutations. The IWRS will use a list of randomization codes generated by a designated vendor [REDACTED].

## 6.4 Blinding and Unblinding

This is a double-blind study.

### 6.4.1 Blinding

The subjects and all site personnel, including the investigator, the site monitor, and the study team, will be blinded with the exception of the following:

- Any site personnel for whom this information is important to ensure the safety of the subject in the event of a life-threatening medical emergency
- Any site personnel for whom this information is important to ensure the safety of the subject and their fetus in the event of a pregnancy
- Vertex Global Patient Safety (GPS) and Regulatory Affairs personnel to satisfy serious adverse event (SAE) processing and reporting regulations
- Unblinded statistician preparing the final (production) randomization list who is not part of the study team
- Vertex Clinical Operations IWRS management
- Vertex Clinical Supply Chain
- IDMC
- Vendor preparing the unblinded analysis for the IDMC
- Vendor analyzing PK samples
- Vertex or vendor conducting the population PK analysis
- Vertex medical monitor may, for matters relating to safety concerns, unblind individual subjects at any time. Such unblindings will be fully documented (see below).

Vertex Drug Metabolism and Pharmacokinetics laboratory personnel will not be involved in the conduct of the study and will be unblinded to the bioanalysis results but will remain blinded to subject number and treatment assignment.

#### Spirometry Data Blinding

Despite treatment blinding, knowledge of the spirometry results has the potential to suggest whether a subject has been administered active study drug or placebo. Therefore, during the conduct of the study, the Vertex study team will have no access to the post-dose spirometry data. The vendor for central reading of the spirometry data will only send the blinded spirometry files (blinded treatment group, with real values for screening and baseline, but with dummy values for all the spirometry assessments after baseline) to Vertex to be used for developing the statistical programs. Furthermore, subjects and their caregiver should not be informed of their study-related spirometry results during the Treatment Period regardless of whether the subject has prematurely discontinued treatment.

#### Sweat Chloride Data Blinding

Despite treatment blinding, knowledge of the sweat chloride data has the potential to suggest whether a subject has been administered active study drug or placebo. Therefore, during the conduct of the study, the Vertex study team will have no access to the postdose sweat chloride data; dummy data will be used to develop statistical programs. During the process of

locking the clinical database, after all study visits have been completed, access to treatment-blinded sweat chloride data will be provided to a small group of individuals (a biostatistician, a statistical programmer, a validation statistical programmer, and a clinical reviewer) who are not part of the Vertex study team. This small group will review the sweat chloride data to ensure there are no significant data issues and will use the blinded data set to refine the statistical programs.

[REDACTED]

#### 6.4.2 Unblinding

At the initiation of the study, the study site will be instructed on the method for breaking the blind. The unblinding method will be either a manual or electronic process.

Unblinding of the individual subject's treatment by the investigator will be limited to medical emergencies or urgent clinical situations in which knowledge of the subject's study treatment is necessary for clinical management. In such cases, investigators should use their best judgment as to whether to unblind without first attempting to contact the medical monitor to discuss and agree to the need for unblinding. If investigators deem that it is not necessary to unblind immediately, they will first attempt to contact the medical monitor to discuss and agree to the need for unblinding. If investigators have tried but are unable to reach the medical monitor, they should use their best judgment, based on the nature and urgency of the clinical situation, and may proceed with unblinding without having successfully reached and discussed the situation with the medical monitor.

Contact information for the medical monitor (or appropriate backup) will be provided in a separate document.

In addition, the Vertex Medical Information Call Center [REDACTED] will answer calls 24 hours a day, 7 days a week, 365 days of the year, and will triage these calls to the study medical monitor or appropriate backup.

If a subject's treatment assignment has been unblinded for a medical emergency or urgent clinical situation, the medical monitor should be notified within 24 hours of the unblinding event. The reason and the date of the unblinding will be documented clearly in the subject's study file. Information about the treatment assignment obtained from the unblinding will be maintained in a secure location with controlled access and will not be shared with sponsor (Vertex), contract research organization (CRO), or any site personnel (other than the

physician treating the subject). In addition, the investigator will consider whether the clinical event that prompted unblinding will be considered an SAE, according to the regulatory definitions or criteria for SAEs, and if so, submit an SAE report to Vertex Global Patient Safety (GPS) or designee, per Section 13.1.2 of the clinical study protocol.

Vertex GPS or designee will also unblind any SAE reports in compliance with regulatory reporting requirements. In addition, the Vertex medical monitor may, for matters relating to safety concerns, unblind individual subjects at any time.

## 7 ANALYSIS SETS

The following analysis sets are defined: All Subjects Set, Randomized Set, Full Analysis Set (FAS), and Safety Set.

The **All Subjects Set** is defined as all subjects who have been randomized or have received at least 1 dose of study drug.

The **Randomized Set** is defined as all subjects who have been randomized.

The **Full Analysis Set (FAS)** is defined as all randomized subjects who carry the intended CFTR mutations (see Section 10.8) and have received at least 1 dose of study drug.

The **Safety Set** is defined as all subjects who received at least 1 dose of study drug.

## 8 STATISTICAL ANALYSIS

### 8.1 General Considerations

All individual subject data for those randomized or exposed to study drug will be presented in data listings. The Schedule of Assessments is provided in Section 10.1. The precision standards are provided in Section 10.6.

**Continuous variables** will be summarized using the following descriptive summary statistics: the number of subjects (n), mean, standard deviation (SD), median, minimum value (min), and maximum value (max).

**Categorical variables** will be summarized using counts and percentages.

**Treatment Emergent (TE) Period** for Treatment Period 1 will correspond to data from the first dose of study drug in the first period to the safety evaluation visit (Safety Follow-up Visit, if subject discontinues treatment in Period 1) or 28 days after the last dose in the same period for subjects who do not have a safety evaluation visit. Similarly, the TE period for Treatment Period 2 will correspond to data from the first dose of study drug in the second period through the Safety Follow-up Visit (SFUV) or 28 days after the last dose in the same period for subjects who do not have an SFUV. The TE period for Treatment Period 1 and Treatment Period 2 will not exceed the day before the first dose of study drug in the extension study for subjects who enrolled into the extension study.

**Baseline Value:** For this crossover study, 2 types of baseline will be defined. The *study baseline* is defined as the most recent non-missing measurement (scheduled or unscheduled) collected prior to the first dose of study drug in the study. The definition will be applied to all

demographics, background, and baseline characteristics and also to efficacy data analyses, including the primary endpoint analysis. In addition, *period baseline* is defined as the most recent non-missing measurement (scheduled or unscheduled) collected before the first dose of study drug in each Treatment Period. For Treatment Period 2, the baseline should be from an assessment measured after the TE period for Treatment Period 1. This definition will be applied to all safety data analysis. For ECG, baseline for Period 1 will be defined as the average of the 3 pretreatment measurements on Day 1. For sweat chloride, the study baseline value will be the mean of assessment values on the left and the right arm at the most recent time point prior to the first dose of study drug in the study. If the result from only one of the arms is available then the result from that arm will be considered as baseline.

**Change (Absolute change) from study baseline** will be calculated as post-baseline value – study baseline value.

**Relative change from study baseline** will be calculated as  $100 \times (\text{post-baseline value} - \text{study baseline value}) / \text{study baseline value}$ .

**Change (Absolute change) from period baseline** will be calculated as post-baseline value – period baseline value.

**Relative change from period baseline** will be calculated as  $100 \times (\text{post-baseline value} - \text{period baseline value}) / \text{period baseline value}$ .

**Unscheduled Visits:** Unscheduled visit measurements will be included in the following:

- (1) derivations of measurements at scheduled visits per specified visit windowing rules below;
- (2) derivations of baseline/last on-treatment measurements;
- (3) derivations of the maximum/minimum on-treatment values and maximum/minimum changes from baseline values for safety analyses;
- (4) data listings where appropriate.

**Visit Windowing Rules:** Section 10.2 defines the windows for protocol-defined visits. The windows will be applied using the following rules for both scheduled and unscheduled visits:

- (1) If no measurement is available within a visit window, the assessment will be considered missing for the visit;
- (2) If there is more than one measurement available within the same visit window, use the following rules:
  - For all efficacy parameters, if there are multiple measurements within a visit window, the record at the scheduled visit will be used. If there are no measurements at the scheduled visit:
    - the record closest to the target day will be used.
    - If there are multiple records with the same distance to the target day, the latest record will be used.
    - Assessments at early treatment termination (ETT) visit will follow the windowing rules for regular visits up to Week 24.

- A safety follow-up visit (SFUV) assessment will follow the windowing rules for regular visits if it falls within the upper boundary of the visit window for Week 8 (period 1) or Week 24 (period 2), or remain as SFUV otherwise.
- For all safety parameters, if there are multiple measurements within a visit window, then 1) the record closest to the target day will be used; 2) if there are multiple records within the same distance from the target day, the latest record will be used; 3) SFUV will not be windowed, instead, used per nominal visit in relevant analyses.

Note: spirometry assessments, BMI, weight, and height will be used for both efficacy and safety purposes. The corresponding measurements will follow visit windowing rules for efficacy.

**Incomplete/Missing data** will not be imputed, unless otherwise specified.

**Outliers:** No formal statistical analyses will be performed to detect or remedy the presence of statistical outliers, unless otherwise specified.

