^j A sweat chloride test must be performed if an eligible sweat chloride value is not available in the subject's medical records. For subjects using a sweat chloride value documented in their medical record to establish eligibility, the sweat chloride test at the Screening Visit is optional.

Table 3-1 Screening Period Assessments – Study VX14-661-108

Event/Assessment	Screening Period (Day -28 Through Day -1)
Coagulation	X
Serum chemistry	X
[REDACTED]	[REDACTED]
[REDACTED]	[REDACTED]
Inclusion/exclusion criteria review	X
Prior and concomitant medications	X
AEs and SAEs	Continuous from signing of the ICF and assent (where applicable) through the Safety Follow-up Visit

AE: adverse event; CF: cystic fibrosis; CFQ-R: Cystic Fibrosis Questionnaire-Revised; CFTR: CF transmembrane conductance regulator; ECG: electrocardiogram; FSH: follicle-stimulating hormone; ICF: informed consent form; [REDACTED]; PE: physical examination; SAE: serious adverse event; [REDACTED]

^k One stool sample will be collected at the clinic or by the subject at home and provided before randomization.

In [Table 3-2](#), all visits are scheduled relative to the Day 1 Visit (first dose of study drug). The Week 2 Visit occurs after 2 weeks of treatment have been completed (i.e., Day 15 [± 3] days). The Week 8 (± 5 days) Visit occurs after 8 weeks of study drug administration have been completed (i.e., Day 57 [± 5 days]). Similarly, during Treatment Period 2, the Day 113, Week 17 Visit is the first dose of study drug for Treatment Period 2. The Week 18 Visit of Treatment Period 2 occurs after 2 weeks of treatment have been completed in Treatment Period 2 (i.e., Day 127 [± 3 days] of the study). The Week 24 (± 5 days) Visit occurs after 8 weeks of study drug administration have been completed in Treatment Period 2 (i.e., Day 169 [± 5 days]).

Table 3-2 Treatment Periods, Washout Period, ETT, and Safety Follow-up Visit Assessments – Study VX14-661-108

Event/Assessment ^b	Treatment Period 1				Washout ^a	Treatment Period 2				ETT Visit ^c	Safety Follow-up Visit 28 days (± 7 days) After Last Dose ^d
	Week 1 (Day 1)	Week 2 (Day 15) (± 3 Days)	Week 4 (Day 29) (± 5 Days)	Week 8 (Day 57) (± 5 Days)	Safety Evaluation Visit Week 12 (Day 85) (± 5 Days)	Week 17 ^a (Day 113)	Week 18 (Day 127) (± 3 Days)	Week 20 (Day 141) (± 5 Days)	Week 24 (Day 169) (± 5 Days)		
Clinic visit	X	X	X	X	X	X	X	X	X	X	X
Inclusion and exclusion criteria review	X					X ^e					
CFQ-R ^f	X		X	X	X	X		X	X	X	X

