8.1.5 Follow-up

The Safety Follow-up Visit assessments are listed in [Table 3-2](#). There will be an outpatient Safety Follow-up Visit 28 days \pm 7 days after the last dose of study drug for subjects who complete study drug treatment and for subjects who prematurely discontinue study drug treatment.

The Safety Follow-up Visit is not required for subjects who complete the Week 24 Visit and have enrolled in an extension study of VX-661 in combination with ivacaftor within 28 days after the last dose of study drug.

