 - o If the dose in the clinic will be more than 6 hours after the subject's scheduled morning dose, the subject should take the morning dose at home, and the evening dose will be administered in the clinic. In this event, all assessments will be collected relative to the evening dose.
7. For visits after the Day 1 Visit, subjects will be instructed to bring all used and unused study drug to the site; study drug will be dispensed at each visit, as appropriate.
8. At the Week 8 Visit, the morning dose of study drug will NOT be administered. The last dose of study drug will be the evening dose administered the day before the Week 8 Visit.
9. At the Week 24 Visit, the morning dose of study drug will NOT be administered. The last dose of study drug will be the evening dose administered the day before the Week 24 Visit.

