13.1.1.3 Documentation of Adverse Events

All AEs will be collected from the time ICF is signed until the following time points:

- For subjects who do not enroll: until time of screen failure (e.g., screen failure, withdrawal of consent)
- For enrolled subjects who have a Safety Follow-up Visit: through the Safety Follow-up Visit
- For enrolled subjects who do not have a Safety Follow-up Visit, through the **earliest** of
 - 28 days after the last dose of study drug
 - The ETT Visit, if that visit is 3 weeks or later following the last dose of study drug ([Section 8.1.6](#))
 - prior to the first dose of study drug in the extension study.

All subjects will be queried, using non-leading questions, about the occurrence of AEs at each study visit. When possible, a constellation of signs and/or symptoms will be identified as 1 overall event or diagnosis. All AEs for enrolled subjects will be recorded in the eCRF and source document. AEs for subjects who are screened but not subsequently enrolled in the study will be recorded only in the subject's source documents. The following data will be documented for each AE:

- Description of the event
- Classification of “serious” or “nonserious”
- Date of first occurrence and date of resolution (if applicable)
- Severity
- Causal relationship to study drug(s)
- Action taken
- Outcome
- Concomitant medication or other treatment given
- Indication of dose limiting toxicity

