## 8.4 Safety Analysis

All safety analyses will be based on the set of data associated with the TE period for Treatment Period 1 and the TE period for Treatment Period 2. Safety analyses will use the Safety Set. Subjects will be analyzed according to the treatment they actually received in a given treatment period. For subjects receiving study drug from more than one treatment group in the same treatment period, the treatment group allocation will be the higher treatment group (TEZ/IVA > IVA monotherapy > Placebo). For safety analysis, the period baseline will be used.

The overall safety profile of study drug will be assessed in terms of the following safety and tolerability endpoints:

- Adverse events
- Clinical laboratory values (hematology, serum chemistry, coagulation studies, vitamin levels, lipid panel, and urinalysis)
- Standard 12-lead electrocardiograms
- Vital signs
- Pulse oximetry
- Postdose ppFEV1 and FEV1 (L) and change from predose (in subjects <18 years at screening).

The safety profile will also include the following safety-supporting data

- predose ppFEV1 and FEV1 (L) across visits
- Weight
- BMI.

Only descriptive analysis of safety will be performed; no statistical testing is planned.

For the purpose of safety analysis, the study period will be further divided into 3 segments per the definition of the treatment emergent (TE) period (Section 8.1):

- The **pre-treatment period** is the period after the informed consent/assent date and before the initial dosing of study drug in the study.
- The **treatment-emergent period** (TE period) is defined in Section 8.1.
- The **post-treatment period** is the period after the last date of TE period for Treatment Period 2 to the date of the last study record in the clinical database or the period between the end of TE period for Treatment Period 1 and the start of TE period for Treatment Period 2. For subjects who do not have Treatment Period 2, the period after the last date

of TE period for Treatment Period 1 to the date of the last study record in the clinical database will be considered as post-treatment period.

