#### **8.4.2 Clinical Laboratory Values**

For treatment-emergent laboratory measurements, the raw values and change from period baseline values for the continuous hematology, chemistry and coagulation results will be summarized in SI units by treatment group at each scheduled time point. For hematology, coagulation and chemistry measurements, the number and percentage of subjects with an abnormal low (<LLN) value and an abnormal high (>ULN) value at each analysis visit will be summarized.

The number and percentage of subjects with hematology, chemistry and coagulation values meeting the defined threshold criteria during the visit window for analysis visits will be summarized by analysis visit. Similarly, the hematology, chemistry and coagulation values meeting the defined threshold criteria during the overall TE period will be presented. The threshold analysis criteria are provided in Section 10.5 (Table 10-7 and Table 10-8).

For all LFT results (alanine aminotransferase [ALT], aspartate aminotransferase [AST], alkaline phosphatase [ALP], direct bilirubin, total bilirubin, and gamma-glutamyl transferase [GGT]), the following additional analyses will be conducted:

- A listing of subjects with elevated LFT results during the TE period will be presented. For each subject in the listing, LFT assessments at all visits during the TE period with elevated LFT will be included.
- For each of the LFTs, mean values ( $\pm$ SD) will be plotted by visit.
- The incidence of LFTs meeting threshold analysis criteria during the TE period against the period baseline threshold criteria will be summarized by treatment group (only worsening of the shift from period baseline will be presented).
- A scatter plot of the maximum ALT value across visits versus the maximum total bilirubin value also will be presented. The ALT and Total bilirubin values will be presented on a logarithmic scale. The graph will be divided into 4 quadrants with a vertical line corresponding to 3xULN for ALT and a horizontal line corresponding to 2xULN for total bilirubin. A similar graph of maximum AST value versus maximum total bilirubin value will be presented as well.

A summary table for the shift from period baseline to the value at Week 8 will be presented by treatment group for vitamin levels and lipid panel. A box plot of vitamin levels and lipid panel will also be plotted against visit.

For amylase and lipase, mean values ( $\pm$ SD) will be plotted by visit.

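### The SAP's whole-day cap on the treatment-emergent period puts the Week 24 pre-dose safety data outside the safety summaries for any subject who starts the extension on the Week 24 Visit day

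*SAP*

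**What the plan says.** **TE period.** SAP 8.1 runs the Period 2 TE period from the first Period 2 dose to the Safety Follow-up Visit, or to 28 days after the last dose if that visit does not take place. It adds that, for extension enrollees, the TE period "will not exceed the day before the first dose of study drug in the extension study for subjects who enrolled into the extension study". Protocol 12.3.1 gives the same definition without this cap. The SAP's introduction says that the SAP governs where its methods differ from the protocol's.

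**Use of the TE period.** SAP 8.4: "All safety analyses will be based on the set of data associated with the TE period" for Treatment Periods 1 and 2. SAP 8.4.2 to 8.4.5 repeat the restriction for the by-visit summaries of laboratory, ECG, vital-sign and oximetry values. Under SAP 8.4.1 an adverse event arising after the Period 2 TE period is a post-treatment event, and Protocol 12.3.4.1 limits the AE tables to treatment-emergent events.

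**Timing around Week 24.** Protocol 10.2 gives no study drug on the morning of the visit: "The last dose of study drug will be the evening dose administered the day before the Week 24 Visit". Protocol 8.1 offers the extension to subjects who complete Week 24. Protocol 8.1.5 waives the Safety Follow-up Visit for completers who "have enrolled in an extension study of VX-661 in combination with ivacaftor within 28 days after the last dose of study drug". Neither section sets a minimum gap or a day for the first extension dose.

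**AE collection.** For enrolled subjects without a Safety Follow-up Visit, Protocol 13.1.1.3 stops collection at the earliest of several points. One of these is "prior to the first dose of study drug in the extension study".

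**The concern.** The purpose of the cap is sound: events and values arising on extension drug should not be credited to this study's regimens. The difficulty is its unit, a whole day. If visit and first extension dose share a date, the cap also removes assessments made earlier that day, about half a day after the last study dose and before any extension drug.

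Week 24 is the end-of-treatment safety visit of Period 2, and Period 2 supplies half of the planned exposure to each regimen. The two periods would also be treated differently. For subjects who go on to the washout, Period 1 TE runs to the Week 12 safety evaluation, so a finding at Week 8 is treatment-emergent. The same finding at Week 24 in a same-day starter is not.

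**Working it through.** **Inputs**
- Period 2 start (Protocol 3): "the Day 113, Week 17 Visit is the first dose of study drug for Treatment Period 2".
- Week 24 Visit (Protocol 3): it "occurs after 8 weeks of study drug administration have been completed in Treatment Period 2 (i.e., Day 169", with a window of 5 days either side.
- Last Period 2 dose: the evening before that visit (Protocol 10.2).
- 34 subjects per sequence, six sequences (Protocol 8.1).

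**Step 1: reproduce the plan's visit day.** 113 + 56 = 169, which matches. Within the period this is day 169 − 113 + 1 = 57. The last dose is on Day 168.

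**Step 2: end of TE.** Let E be the day of the first extension dose. With no Safety Follow-up Visit, the uncapped end is 168 + 28 = Day 196. Under SAP 8.1, TE end = min(196, E − 1).

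| First extension dose (E) | TE end | Week 24 day (169) inside TE? |
|---|---|---|
| Day 169 | Day 168 (period day 56) | No |
| Day 170 | Day 169 (period day 57) | Yes |
| Day 176 | Day 175 | Yes |
| Day 196 | Day 195 | Yes |

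Only a same-day start triggers the problem, and it does so anywhere in the visit window: a visit and start on Day 164 gives TE end 163, and on Day 174 gives 173.

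**Step 3: what is left for a same-day starter.**
- Coagulation, vitamins and lipids are scheduled in Period 2 only at Week 17 (pre-dose baseline) and Week 24, apart from termination or follow-up visits. No scheduled on-treatment value falls in TE. For vitamins and lipids SAP 8.4.2 plans this output: "A summary table for the shift from period baseline to the value at Week 8 will be presented by treatment group". SAP Table 10-3 maps Week 24 to that analysis visit, so the value has an intended place from which the cap removes it.
- For chemistry and hematology the last scheduled TE value is Week 20, period day 141 − 113 + 1 = 29, instead of period day 57.
- In SAP 8.4.1.8 the AE interval after 8 weeks runs from period day 57 to the end of TE. At the nominal visit day TE ends on day 56, so the interval is empty.

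**Step 4: size.** Each treatment appears in four of the six sequences, so 4 × 34 = 136 planned exposures, of which 2 × 34 = 68 are in Period 2. If a fraction f of Period 2 subjects starts the extension on the visit day, 68 × f exposures per treatment drop out, a share of 68f/136 = f/2. The value of f is not in the documents.

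| Assumed f | Exposures per treatment | Share of 136 |
|---|---|---|
| 0% | 0 | 0% |
| 10% | 6.8, about 7 | 5% |
| 25% | 17 | 12.5% |
| 50% | 34 | 25% |

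These counts use planned numbers without dropout.

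**The case against.** **The trigger is not documented.** First-dose timing belongs to the extension protocol, which is not among the documents, and the 28-day rule concerns enrolment. If dosing starts one day later, nothing is lost. This stands: the point is conditional, and the range must include zero.

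**The data are not lost.** A reader might infer that all Week 24 safety data disappear. They do not. Individual data and post-treatment AEs are listed, and the listing of SAEs and deaths carries a TE flag. Urinalysis was only ever to be listed, so no urinalysis summary is affected. Predose spirometry, weight and BMI follow the efficacy windows, and SAP 8.5 summarises them by post-baseline visit with no TE condition stated there. The primary efficacy analysis uses all measurements up to Week 8 of each period. All of this stands.

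**By-visit threshold tables may escape.** SAP 8.4.2 to 8.4.4 describe them by visit window, separately from the overall TE tables, and Table 10-3 has no extension cut-off. This stands in part. The general rule in SAP 8.4 points to exclusion, and the by-visit summaries of values and changes are explicitly for treatment-emergent measurements.

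**No contradiction over AEs.** A reader might infer that SAP 8.1 and Protocol 13.1.1.3 contradict each other. The protocol section governs how long AEs are collected; the SAP governs how they are classified, and a collected event may properly be post-treatment. The protocol text to compare is the TE definition in 12.3.1, which lacks the cap.

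**A date rule suits date-only data.** AE onset is recorded by date, and a date cap reliably keeps extension events out. That is a fair reason for care with same-day AEs. It is no reason to exclude visit assessments known to precede the dose.

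**Conclusion.** The concern holds in a limited, conditional form. As written, SAP 8.1 misclassifies the pre-dose Week 24 laboratory, ECG, vital-sign and oximetry values of any subject who starts the extension that day, together with any AE starting that day before the extension dose. Nothing in the SAP makes an exception.

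The effect lies between 0% and 25% of planned exposures per treatment for same-day rates from 0% to 50%. That rate is an assumption, so the documents do not show that the loss is large. Each treatment has the same planned number of Period 2 exposures and safety analyses are descriptive, so the expected cost is end-of-treatment safety information and some under-counted events, not a bias between arms. Excluding what happens after the first extension dose remains correct.

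**What to change.** Replace the cap in SAP 8.1 with wording to this effect:

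> For subjects who enter the extension study, the Treatment Period 2 TE period ends no later than immediately before the first extension dose. Week 24 Visit assessments made before that dose are within the TE period, even if on the same calendar day. An AE with onset on that date is a Period 2 TEAE if it was recorded in this study as starting before the first extension dose (Protocol 13.1.1.3); otherwise it belongs to the extension study.

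The cost is a short SAP edit and a date/time condition in the programs before database lock. The small downside is that AE onset carries a date and no time, so same-day events must be assigned by the study that recorded them, with a check that none is counted in both. If no subject starts the extension on the visit day, no Week 24 result changes.
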